#### 4.2.8 Safety

##### **Serious Adverse Events (SAE)**

All SAEs starting after the first dose of therapy, or within 30 days after stopping therapy, will be included in the summary table providing frequency (the same SAE occurring more than once to the same patient will be taken into account only once).

SAEs will be presented by System Organ Class (SOC) and Preferred Term (PT).

SAEs leading to death and SAEs leading to treatment discontinuation will be also summarised separately.

Any SAEs occurring before starting treatment with AZD9291 will be included in the data listing but will not be included in the summary tables of SAEs.

##### **Adverse Events of Special Interest (AESI)**

Summaries of the AESIs will include number (%) of patients who have:

- At least one AESI
- At least one AESI related to study medication. If causality is missing, assume that the AESI is related.
- At least one AESI leading to dose modification (reduction/interruption)
- At least one AESI leading to discontinuation

A summary of duration (days) of AESI will be provided for all events and this will be supported by summaries of events which have an end date, ongoing AESIs at death and, separately, at study discontinuation. All durations will be calculated.

Duration of Ongoing AESIs will be calculated using study discontinuation date as end date.

Duration of fatal AESIs will be calculated using death date collected on death form as end date.

Summary statistics of Time of Onset (days) from study treatment to start of AESI will also be provided for all AESIs.

Summary tables of AESIs providing the number (%) of patients experiencing any of the specified terms by maximum CTCAE grade will be also produced.

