### **Duration of IP administration**

Patients may continue to receive AZD9291 as long as they continue to show clinical benefit, as judged by the investigator, and in the absence of discontinuation criteria (see section 4.3).

Enrolment will be closed within 6 months of market license approval in that country or at national reimbursement, whichever is sooner.

The study will be closed in each participating country as soon as possible following national reimbursement of AZD9291 in that country (up to a max of 90 days post reimbursement).

Patients withdrawing from the treatment prior to national reimbursement will be followed up as part of this study until death or lost to follow-up.

At national reimbursement patients still on treatment will be transitioned to commercial supply as long as the patient is benefitting from treatment as per investigator assessment, and in accordance with national regulations in the countries where the study is conducted.

In the event that national reimbursement should not be granted following a reasonable time after market license approval in the country, the study will be closed in a maximum period of 18 months after the last patient is enrolled in that country. Contingencies will be made locally to ensure continued drug supply for patients who are still deriving benefit from AZD9291 at that time.

If applicable, timelines for conversion to commercial drug will be agreed with local bodies which may include regulatory agencies, ethics committees, and institutions.

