## **9.4 Methods for statistical analyses**

All analyses will be performed on the FAS population. No statistical tests will be performed, the statistical analyses will be descriptive.

Efficacy analyses will be repeated by cohorts defined by number and type of previous treatment lines and by other pre-defined subgroups of interest as pre-specified in the SAP.

Data will be summarized using descriptive statistics as appropriate. Continuous variables will be summarised by the number of observations (n), mean, standard deviation (SD), median, quartiles (Q1 and Q3), minimum, and maximum. Categorical variables will be summarised by frequency counts and percentages for each category.

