### 2.1 Definition of analysis set

#### Full Analysis Set (FAS)

The full analysis set will include all patients who received at least one dose of study treatment (i.e. with at least one start date in the Administration of the Study drug page in the CRF).

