#### ***Subgroup analyses***

Overall summary of AEs will be analysed in the following subgroups of the FAS:

- Age at enrolment (<75 ; ≥75 years of age)
- Baseline WHO Performance Status (<2; =2)
- Sample Type (Plasma ; Tissue ; Other)
- Brain/leptomeningeal metastases status at baseline (Present ; Absent ; Not Done)

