##### **Serious Adverse Events (SAE)**

The following summaries will be provided for all SAEs as defined in the SAP section 4.2.8:

- number (%) of patients reporting SAEs assessed as causally related to AZD9291 by System Organ Class (SOC) and Preferred Term (PT). If causality is missing, assume that the SAE is causally related.
- number (%) of patients reporting SAEs by SOC, PT and maximum CTCAE grade.
- number (%) of patients reporting SAEs leading to dose modification by SOC and PT.

A listing of all SAEs will be produced. SAEs occurring before starting treatment with AZD9291 included in the data listing will not be included in the summary tables of SAEs.

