##### ***Subgroup analyses***

Overall summary of AESIs and SAEs will be analysed in all subgroups of the FAS as defined in section 4.2.8 of the SAP.

[figure not shown]
[figure not shown]
A summary table of AEs with CTCAE grade  $\geq 3$  providing the number (%) of patients experiencing any of the specified terms will be also produced.

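### SAE and AESI results are crude percentages of the FAS, with no allowance for patients still on drug when their country closes, so they understate on-drug cumulative risk

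*SAP*

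**What the plan says.** - **Measure.** SAP 4.2.8 says of AESIs: "Summaries of the AESIs will include number (%) of patients who have" at least one event, one related event, and so on. For SAEs: "All SAEs starting after the first dose of therapy, or within 30 days after stopping therapy, will be included in the summary table providing frequency", each event counted once per patient. The SAP addendum, section 4.1.2, keeps the same form, for example "number (%) of patients reporting SAEs by SOC, PT and maximum CTCAE grade".
- **Denominator.** SAP 2.1: "The full analysis set will include all patients who received at least one dose of study treatment", whatever the length of follow-up.
- **Subgroups.** SAP 4.2.8: "Overall summary of AEs will be analysed in the following subgroups of the FAS", namely age 75, WHO performance status, sample type and brain/leptomeningeal metastases. The addendum carries this over: "Overall summary of AESIs and SAEs will be analysed in all subgroups of the FAS as defined in section 4.2.8 of the SAP".
- **Closure.** Protocol synopsis, Duration of IP administration: "At national reimbursement patients still on treatment will be transitioned to commercial supply". Protocol 4.4 and 10.2.4 close each country at most 90 days after reimbursement. Without reimbursement, 10.2.4 closes it at most 18 months after its last patient is enrolled. Nothing is collected after closure. Enrolment may run until reimbursement, so a late entrant can be observed for 90 days or less while continuing the drug.
- **Efficacy handling.** SAP 3.1.3 censors TTD at transition to commercial supply. SAP 4.2.7 classes these patients as prematurely censored for OS and summarises their follow-up.
- **Safety handling.** The readable text has no exposure-adjusted rate, Kaplan-Meier or cumulative-incidence estimate for any safety endpoint. Redacted parts are not counted as gaps.

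**The concern.** A patient who moves to commercial supply stays in the denominator at full weight, but can no longer add an event while still taking the drug. The percentage is then neither the risk over a course of treatment nor the risk by a fixed time. It depends partly on when each country granted reimbursement. Safety is named with efficacy in the primary objective, and in a descriptive study the estimate is itself the result. The same percentages will be set side by side for older patients, WHO status 2 and patients with brain metastases, without person-time for those groups.

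**Working it through.** **1. The plan's own figure.** The only design calculation concerns OS: N = 3500, median 25 months, 1983 events. Median × exp(±1.96/√events) = 25 × exp(±1.96/√1983) = 23.92 to 26.12 months, against 23.9-26.1 stated. Maturity is 1983/3500 = 56.7% (57% in SAP 1.3). No safety rate or safety precision is planned, so the event rate and time on drug below are assumptions.

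**2. Model.** Time on drug is exponential with hazard m = ln 2/13 = 0.0533 per month. The AESI hazard h(t) is either constant at 0.5% per month, or early-peaking (three times that for 3 months, then half). G(t) is the probability that the country is still open at time t.

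- Crude % = ∫ h(t) exp(−H(t) − m t) G(t) dt, where H is the cumulative hazard.
- Constant h, no closure: h/(h+m) = 0.005/0.0583 = 8.6%.
- Constant h, closure uniform on (a,b), with k = h+m: (h/k)[1 − (e^(−ka) − e^(−kb))/(k(b−a))]. For (0,30): 8.57% × (1 − 0.472) = 4.5%.
- Constant h, closure fixed at c: (h/k)(1 − e^(−kc)). For c = 30.2: 8.57% × 0.828 = 7.1%.
- OS maturity implied by each closure pattern uses the same expressions without the h/k factor, and with λ = ln 2/25 in place of k.

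| Closure (months from first dose) | Implied OS maturity | Crude %, constant (shortfall) | Crude %, early-peaking (shortfall) |
|---|---|---|---|
| none | n/a | 8.6 | 7.7 |
| fixed 30.2 | 57% | 7.1 (17%) | 6.9 (10%) |
| uniform 3-65 | 56% | 6.6 (23%) | 6.7 (13%) |
| uniform 0-30 | 32% | 4.5 (47%) | 5.5 (29%) |
| uniform 0-18 | 21% | 3.3 (62%) | 4.7 (39%) |

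Shortfalls are relative to the no-closure row, from unrounded values.

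**3. Shorter treatment.** Take the median PFS of 9.6 months (Protocol 1.2) as a proxy for time on drug. The constant-hazard figures are then 6.5% without closure, 4.0% for uniform 0-30 and 3.0% for uniform 0-18. The two patterns near planned maturity give 5.8% and 5.4%, shortfalls of 10% and 16%.

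**4. Cross-check by simulation.** Median 9.6 months on drug, 1 month of follow-up after it, uniform entry, true on-drug incidence 3% or 25%, hazard constant or early-loaded (Weibull shape 0.5). With closure 3 months after last entry (accrual 6 to 24 months), the crude figure captures about 35-85% of the true incidence. With closure 18 months after last entry (accrual 12 or 40 months), it captures 82-98%.

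**5. Is a rate enough?** With constant hazard, the rate is 0.50 per 100 patient-months whatever the closure. With the early-peaking hazard of step 2, it is 0.45 with no closure, 0.61 for uniform 0-30 and 0.74 for uniform 0-18. Under uniform 0-30, two subgroups with that identical hazard and median TTD of 6 and 13 months show about 0.74 and 0.61, so the shorter-treated one looks about 22% worse.

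**6. Subgroups (constant hazard, simulation of step 4).**
- Equal hazard of 5 per 100 patient-years, median treatment 4 v 14 months: 2.8% v 8.1% without closure, but 2.1% v 3.0% with 12-month accrual and closure 3 months later. Closure narrows the gap.
- Double the hazard and half the treatment time (10 per 100 patient-years and 5 months, against 5 and 10), same closure: 4.5% v 2.9%. The two-fold hazard ratio shows as 4.46/2.86 = 1.6. On-drug risk without closure, h/(h+m), would be about 5.7% in both groups (ignoring the 30-day window), so this is attenuation of the hazard ratio.

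**The case against.** The study is single-arm and descriptive: "No statistical tests will be performed, the statistical analyses will be descriptive". No decision rule uses these percentages, n (%) is a correct count of what was observed, and the SAP does not call it a fixed-time or whole-treatment risk. The SAP also gives context: counts of commercial transitions (4.2.1), exposure classes and a time-on-treatment plot (4.2.6), AESI onset times (4.2.8), and Kaplan-Meier TTD in all four safety subgroups (4.2.7). The addendum adds SAE and AESI listings.

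All of that stands, and it limits the weight of the point. It does not remove it. Onset times describe only patients who had an event. Exposure is summarised for the FAS and for discontinued patients, not by safety subgroup. TTD by subgroup shows who was treated longer, but does not turn a crude percentage into a risk.

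Four stronger readings are tempting, and the documents do not support them.
- *Closure roughly halves the reported risk.* The scenarios that give 47-62% imply OS maturity of 32% and 21%, against 57% planned. The planning figure may not allow for early reimbursement, but it is the only follow-up figure available.
- *Short-treated subgroups will look safer, or contrasts will reverse.* No document says that observation differs by subgroup. At equal hazard, a shorter course does carry less on-drug risk, and closure narrows that gap. With a higher hazard in the short-treated group, that group still looked worse.
- *Any early end of treatment is understatement.* Stopping for progression or death is a competing event. Only closure while the patient is on drug removes events that belong to the on-drug risk.
- *Events per patient-month solve it.* Step 5 shows that they do not when events come early. Exposure in SAP 3.2.4 also ends at the last dose, whereas SAEs count for 30 days more.

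**Conclusion.** The point holds in direction. The planned SAE and AESI percentages make no allowance for closure on drug, although the SAP does so for TTD and OS, and they therefore understate on-drug cumulative risk. The size cannot be fixed from the documents. Under 0.5% per month and median TTD of 13 months, the relative shortfall is about 10-23% with closure consistent with planned OS maturity and about 30-60% with quick closure. It is smaller with shorter treatment or later closure, and when events come early. Distortion of subgroup contrasts, usually attenuation, is conditional on treatment or observation time differing between subgroups, which is plausible but undocumented. This calls for an added estimator; the planned counts remain valid as counts.

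**What to change.** - Keep n (%) as planned.
- Add Aalen-Johansen cumulative incidence at 3, 6 and 12 months (already SAP time points for efficacy) for ILD/pneumonitis, QTc events and any SAE, overall and in the four safety subgroups. Censor at commercial transition or country closure. Treat as competing events death without the event, and the end of the event window (30 days after last dose) without the event.
- State that window once and apply it to AESIs too, for which SAP 4.2.8 gives none. SAP 3.2.1 and Protocol 9.4.3 run to progression if later, whereas SAP 4.2.8 summarises SAEs to 30 days, so the passages need reconciling.
- Report person-time on the same window by safety subgroup. Label exposure-adjusted rates as supportive, because they also depend on closure when events come early.

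Cost: a few more outputs and the derivation of time at risk on the event window, which is not the exposure in SAP 3.2.4. No new data are needed.

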**Table 4 Study Plan**

	Screening/ Enrolment visit		Treatment visit	Treatment Discontinuation	30 day follow up (c)	Progression Follow-up (e)	Survival follow up (g)
	-28 days	Day 1	(every 6 weeks)			(every 6 weeks)	(every 6 weeks)
Windows (days)			+/- 7 days	+/- 7 days	+/- 7 days	+/- 7 days	+/- 7 days
Informed Consent	X						
Inclusion/Exclusion criteria check	X						
Complete enrolment form	X						
Confirm T790M mutation	X (d)						
Patient demographics	X						
Medical history	X						
Disease characteristics	X						
Cancer treatment history	X						
Concomitant medications	X	X	X	X			
Complete blood count	X		If clinically indicated or per institutional standard of care	If clinically indicated or per institutional standard of care			
Biochemistry in blood and urine	X		If clinically indicated or per institutional standard of care	If clinically indicated or per institutional standard of care			
Pregnancy test	X (h)						
Physical examination	X			X			
WHO Performance status	X		X	X			
Weight	X		X	X			
ECG recording	X		If clinically indicated or per institutional standard of care	If clinically indicated or per institutional standard of care			
Visual test (slit-lamp)	X		If clinically indicated or per institutional standard of care	If clinically indicated or per institutional standard of care			
Dispense AZD9291 (IVRS/IWRS)		X AZD9291 start-dose	X AZD9291 re-supply				
AZD9291 dosing (daily): - current dose; dose adjustment;			X				

	Screening/ Enrolment visit		Treatment visit	Treatment Discontinuation	30 day follow up (c)	Progression Follow-up (e)	Survival follow up (g)
interruption/discontinuation reason for change							
Drug accountability			X				
Investigator-reported efficacy			X	X		X	
SAE, including overdose and pregnancy reporting (a)(f)		X	X	X	X	X	
Adverse event of special interest (b) AEs leading to dose modification including drug discontinuation			X	X	X	X	
Reason for withdrawal				X			
Survival status							X

- (a) Following AZD9291 discontinuation, SAEs considered related to study procedures should continue to be collected until disease progression
- (b) ILD/pneumonitis-like event; cardiac event (see section 6.6.1 and 6.6.2).
- (c) A 30 day post last dose follow up contact (visit or by telephone) should be made with the subject to collect new SAEs, andAESI and to follow up on any ongoing SAEs andAESI.

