#### **Follow-up of unresolved adverse events**

Any AEs that are unresolved at the subject's last visit in the study are followed up by the investigator for as long as medically indicated, but without further recording in the CRF. AstraZeneca retains the right to request additional information for any subject with ongoing AE(s) at the end of the study, if judged necessary.

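### Ongoing AESIs are given durations to study discontinuation, so the all-events duration summary counts time with no AESI record and treats open events as complete

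*SAP*

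**What the plan says.** **SAP 4.2.8, AESI paragraph.** The plan says that "A summary of duration (days) of AESI will be provided for all events", and that "this will be supported by summaries of events which have an end date, ongoing AESIs at death and, separately, at study discontinuation". It adds that "All durations will be calculated", and fixes the end date of unresolved events: "Duration of Ongoing AESIs will be calculated using study discontinuation date as end date". Fatal AESIs end at the date of death. No event is treated as censored.

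**SAP Addendum 01, section 4.1.2.** This adds a table of AESIs by outcome and a listing of all AESIs. It does not change the duration rule.

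**Protocol Table 4.** AESIs share a row with "AEs leading to dose modification including drug discontinuation". The row is marked at treatment visits, treatment discontinuation, the 30-day follow-up and progression follow-up. It is blank under survival follow-up, where survival status is the only item marked. Footnote (c) reads: "A 30 day post last dose follow up contact (visit or by telephone) should be made with the subject"; its purpose includes following up ongoing AESIs. Footnote (e) limits progression follow-up to patients who stopped treatment without having progressed. Footnote (g) runs survival follow-up every 6 weeks to the end of the study.

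**Protocol 4.4.** For withdrawn patients who agree, safety follow-up runs to 30 days after the last dose. Survival follow-up comes after that, with progression follow-up if the patient has not progressed.

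**The concern.** The end date assigned to an open AESI is a date on which AESI status need not have been recorded. Survival status is planned up to study discontinuation, so that date is a natural censoring date for OS. AESI status is not planned that far for every patient.

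Two different errors then enter one summary:

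- **Unobserved time counted as event time.** The patient has progressed and stopped treatment, and the AESI was open at the 30-day contact. Everything from that contact to study discontinuation is counted as AESI duration.
- **Truncated time counted as complete.** The patient is still under AESI recording at study end. The event is cut off there and averaged with resolved events.

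The first can make durations too long and the second makes them too short, so the all-events figure has no clear meaning. At stake is how long ILD/pneumonitis-like and QTc events appear to last. These are the only two AESI categories the SAP defines, and safety is part of the study's primary objective.

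The rule also departs from the SAP's own practice. Section 3.1.2 censors PFS at the latest disease assessment, and section 4.1.1 says that missing data other than partial dates are not imputed.

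**Working it through.** The documents give no AESI duration, AESI rate or proportion ongoing, so there is no stated figure to reproduce. The check compares the rule with the collection schedule and then illustrates the size.

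**Step 1. Rule against schedule, by patient situation**

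| Patient with an open AESI | Last planned AESI record | End date under SAP 4.2.8 | Effect |
|---|---|---|---|
| Progressed and stopped treatment | 30-day contact | Study discontinuation | Unrecorded time counted as AESI time |
| Stopped without progression, still in progression follow-up | Progression follow-up visits | Study discontinuation | Truncated, treated as complete |
| Still on treatment at study end, including beyond progression | Treatment or discontinuation visits | Study discontinuation | Truncated, treated as complete |

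**Step 2. Rough length of the unrecorded interval**

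Inputs: assumed median OS 21-25 months (Protocol 9.5, SAP 1.3); preliminary median PFS 9.6 months from an earlier study (Protocol 1.4.2); 30.4375 days per month (SAP 4.1).

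Interval = (median OS - median PFS) x 30.4375 - 30

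- OS 21 months: 11.4 x 30.4375 - 30 = 317 days
- OS 23 months: 13.4 x 30.4375 - 30 = 378 days
- OS 25 months: 15.4 x 30.4375 - 30 = 439 days

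A difference of medians is only a guide, and it ignores study closure.

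**Step 3. Simulation with closure**

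Settings: 400,000 patients; exponential PFS with median 9.6 months; exponential survival after progression, set to give median OS of 21 or 25 months; AESI recording ending 30 days after progression; study discontinuation at death or closure, whichever is earlier. The planning assumption of 58 months with accrual over 40 months gives 58 - 40 = 18 to 58 months of potential follow-up. Closure at 6 and 12 months is an assumption standing for early country closure after reimbursement.

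Added days in the all-events mean = share of AESIs ongoing x mean gap. This compares the SAP rule with ending the same events at their last recorded status.

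| Closure after first dose | Mean gap, days (OS 21 / 25) | Added at 5% ongoing | Added at 10% | Added at 20% |
|---|---|---|---|---|
| 6 months | 20 / 21 | 1 / 1 | 2 / 2 | 4 / 4 |
| 12 months | 69 / 78 | 3 / 4 | 7 / 8 | 14 / 16 |
| 18 months | 123 / 145 | 6 / 7 | 12 / 15 | 25 / 29 |
| 38 months | 249 / 325 | 12 / 16 | 25 / 32 | 50 / 65 |
| 58 months | 296 / 409 | 15 / 20 | 30 / 41 | 59 / 82 |

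The shares ongoing are assumed. The simulation gives patients with an open AESI the same PFS and OS as everyone else, and it ignores treatment beyond progression, which would shorten the gap.

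**Step 4. The median**

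Suppose fewer than half of the events are ongoing and their recorded durations already exceed the overall median. Extending them further then leaves the median unchanged. It moves only as far as ongoing events are pushed across it.

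**The case against.** **The SAP already separates events by status.** This stands in part. Resolved events and events ongoing at death or at study discontinuation have their own summaries, and the addendum adds outcomes and a listing. A reader can see how many end dates were assigned. But the ongoing summary uses the same assigned dates, and the all-events figure stays uncorrected.

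**The affected group is narrow.** This stands. Patients who stop without progression remain under AESI recording in progression follow-up. This may include many who stop for confirmed ILD. Treatment may continue beyond progression (Protocol 4.3.1), with AESIs recorded at treatment visits. Patients on treatment at national reimbursement move to commercial supply, which leaves little or no gap. A reader might infer that every ongoing AESI gains unrecorded months; the schedule does not support that.

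**The protocol does not rule out updating an AESI end date during survival follow-up.** True, but nothing plans it. The rule that unresolved events are "followed up by the investigator for as long as medically indicated, but without further recording in the CRF" is weak evidence either way, because it applies after the patient's last study visit. The finding rests on Table 4 and Protocol 4.4.

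**Duration is a minor output.** This largely stands. Protocol 9.4.3 does not mention it, and the addendum's overall safety summary contains patient counts only. A reader might infer that a main safety result is wrong; the documents do not give duration that rank.

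**The size is assumed.** This stands. A reader might also take the whole difference between the all-events mean and the resolved-only mean as error. That compares unlike groups: unresolved events are expected to last longer, and part of each assigned duration was observed.

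**Conclusion.** The concern holds in limited form. The end-date rule and the collection schedule do not match. The all-events summary counts time without AESI status as AESI time for patients who have progressed and stopped treatment, and it treats truncated durations as complete for patients still under AESI recording.

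The size cannot be derived from the documents. With 10% of AESIs ongoing, the illustration adds about 2-8 days to the mean for closure at 6-12 months and about 12-41 days for closure at 18-58 months. These figures measure unrecorded time that is counted, not the error against true duration, because some of those events may really have continued. Truncation works in the opposite direction and is not quantified here. The documents do not show that the median is materially wrong.

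Only one planned descriptive safety summary is affected. AESI incidence, OS, PFS, TTD and response rate do not use this rule. The rule is wrong as written, with low severity.

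**What to change.** Replace the all-events duration summary in SAP 4.2.8 with a Kaplan-Meier or cumulative incidence estimate of time from AESI onset to resolution:

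- Censor ongoing events at the last visit or contact at which AESI status was recorded, not at study discontinuation.
- Treat fatal AESIs as never resolved.
- Treat death from another cause with the AESI still open as a competing event. Cumulative incidence is the natural form where such deaths occur.
- Show counts of resolved, ongoing and fatal events, and of deaths from another cause.

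Keep the resolved-only summary already planned. If events are few, report resolved-only durations with counts of ongoing and fatal events instead.

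Cost: revised SAP wording, one derived date and one table. The documents define no variable for the last AESI status date, so it must be derived from the dates of the visits and contacts at which Table 4 marks AESI collection. No new data collection is needed.
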